11 STUDY TREATMENT EXPOSURE AND TREATMENT COMPLIANCE

A summary of exposure will be presented using the safety population for each treatment group and will include descriptive statistics of the number of days treated for each treatment group. For each treatment, compliance will be calculated as follow:

$$\frac{\text{Number of doses taken}}{\text{Number of days between the last dose date and the first dose date} + 1} \times 100$$

Descriptive statistics for compliance will be presented for each treatment group. Frequency distribution will also be presented for the following categories: < 80%, [80% - 120%] and > 120%.

Exposure and compliance will be displayed in a listing of study treatment administration.

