7.1 Discontinuation

Subjects who discontinue the study after the first dose will be asked, if they agree, to come for a last assessment (ET visit). Subjects who are discontinued for safety reasons may be asked to come for additional follow-up visits, at the investigator's discretion, after the ET visit to ensure appropriate medical care and AEs follow-up.

Subjects who did not complete the study for reasons other than safety, or have demonstrated significant noncompliance to study treatments based on IP accountability (define as subject who received < 80% or > 120% of the scheduled doses during the study treatment period) will be evaluated by the principal investigator or designee at each visit and may potentially be replaced.

Subjects who discontinue may be replaced at discretion of the sponsor.

Reasons for discontinuation include the following:

- The investigator decides that the subject should be withdrawn. If this decision is made because of a SAE, the study product is to be discontinued in that subject immediately and appropriate measures are to be taken. The investigator will notify the sponsor immediately.
- The attending physician requests that the subject be withdrawn from the study.
- The subject, for any reason, requires treatment with another therapeutic agent that has been demonstrated to be effective for treatment of the study indication. In this case, discontinuation from the study occurs immediately upon introduction of the new agent.
- The subject is lost to follow-up. In this case, a reasonable attempt to contact the subject and ascertain his or her status must be made, and these attempts must be documented.
- The subject becomes pregnant at any time during the study.
- Other: the subject may withdraw from the study for any other reason, including withdrawal of consent.
- The sponsor or regulatory authorities, for any reason, stop the study. In this case, all subjects will be discontinued from the study. The investigator will immediately, on discontinuance of the study by the sponsor, in its entirety or at a clinical trial site, inform both the subjects and the research ethics board of the discontinuance, provide them with the reasons for the discontinuance and advise them in writing of any potential risks to the health of subjects or other persons.

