4.2 Per-Protocol Population

This population will include all subjects who were randomized, who received at least one dose of study product, with no major protocol deviations, and who provided evaluable data for the primary endpoint at Week 16. All subjects will be analyzed according to the treatment group that they actually received during Part A.

The protocol deviations will be presented in a listing and summarized by category. Upon sponsor's review, the listing will also include a flag indicating whether each deviation is considered important or not. Important deviations will be interpreted as major and will result in excluding the related subject from the Per-Protocol Population. This exercise will be done prior to the database lock, on blinded data.

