5.7 Handling of Retests, Unscheduled Visits, and Early Termination Data

When retests measurements are done, the retest measurement will be considered for the summary analysis. All data from retest visits will be listed.

For Safety Data, unscheduled measurements will not be summarized in by-visit summary tables or figures. However, data from unscheduled visits will be listed.

Early Termination (ET) visit assessments will be summarized as a separate visit in by-visit outputs.

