7.2 Protocol Deviations

The number of events and the number and percentage of subjects with at least one major protocol deviation will be summarized by deviation category and treatment group using the safety population. A listing of all major protocol deviations will also be provided.

The protocol deviations in the study will be evaluated on a case to case basis and will be categorized as major or minor. A major protocol deviation is defined as any deviation that may affect the efficacy outcome or subject safety or subject's right. Subjects having major protocol deviation will be finalized prior to the data base lock.

PPD	STATISTICAL ANALYSIS PLAN, Version Final 1.0
Protocol Number: ASN002AD-202 V6.0	Sponsor: Asana BioSciences, LLC

Following are some potential major protocol deviations.

- Violation of major Inclusion /Exclusion Criteria Assessment
- Treatment compliance of <80% or >120%
- Violation of assessment of efficacy parameter
- Violation of visit scheduling.

A subject will be considered non-compliant for the overall study treatment if the subject is non-compliant in Part A.

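### SAP 11 measures compliance over the subject's own first-to-last-dose span, with no Part A cut-off, so it cannot register dosing that stops before Week 16

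*SAP*

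**What the plan says.** SAP 11 introduces the formula with "For each treatment, compliance will be calculated as follow". The numerator is the number of doses taken. The denominator is "Number of days between the last dose date and the first dose date", plus one. The section gives no start or stop date for Part A. The result is tabulated for the safety population as below 80%, 80–120%, and above 120%.

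Protocol 7.1 uses the same two limits with a different denominator. A significantly non-compliant subject is one who "received < 80% or > 120% of the scheduled doses during the study treatment period".

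SAP 7.2 lists compliance outside 80–120% among the potential major deviations and adds: "A subject will be considered non-compliant for the overall study treatment if the subject is non-compliant in Part A". Under SAP 4.2, deviations judged important count as major and remove the subject from the per-protocol population. That population is separately restricted to subjects "who provided evaluable data for the primary endpoint at Week 16". SAP 5.7 keeps early-termination data apart from Week 16: "Early Termination (ET) visit assessments will be summarized as a separate visit in by-visit outputs".

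SAP 3.5, which lists the changes from the protocol, does not mention a change in the compliance definition.

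**The concern.** The same 80–120% limits are applied to two different quantities. Against scheduled doses, stopping early lowers compliance. Against the subject's own dosing span, it does not, because the denominator stops growing on the day dosing stops. The SAP formula does detect missed doses scattered between the first and last dose. It does not detect a gap at the end.

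The Part A rule in SAP 7.2 also has no formula behind it. SAP 10 splits concomitant medications at Week 16, but SAP 11 makes no such split. Major deviations are settled before database lock on blinded data, and Part A is locked once every subject has passed Week 16. By then the earlier enrollees are dosing in Part B, so their last dose date lies outside the period that is meant to decide the matter.

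Two outputs are at stake: membership of the per-protocol set, which supports the primary result, and the compliance table itself.

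**Working it through.** The documents report no compliance figure to reproduce, so the check compares the two definitions on the same dosing histories.

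**Inputs**
- Part A is 16 weeks of once-daily dosing (SAP 3.3). Scheduled doses before the Week 16 visit on Day 113: 16 × 7 = 112.
- The lower limit is 80% (Protocol 7.1, SAP 7.2): 0.80 × 112 = 89.6, so 90 doses are needed.
- SAP compliance = doses taken / (last dose date − first dose date + 1).
- Scheduled-dose compliance for Part A = doses taken / 112.

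**Daily dosing from Day 1, then a stop**

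| Last dose | SAP formula | Share of 112 scheduled |
|---|---|---|
| Day 28 | 28/28 = 100% | 25.0% |
| Day 56 | 56/56 = 100% | 50.0% |
| Day 84 | 84/84 = 100% | 75.0% |
| Day 85 (Week 12 visit) | 85/85 = 100% | 75.9% |
| Day 89 | 89/89 = 100% | 79.5% |
| Day 90 | 90/90 = 100% | 80.4% |

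The SAP value is constant. Against scheduled doses, every stop on or before Day 89 falls below the limit.

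**Visit window.** Week 16 may fall two days either side, giving 110 to 114 scheduled doses and a limit of 88.0 to 91.2. A last dose on Day 85 is then 85/110 = 77.3% to 85/114 = 74.6%, below 80% throughout.

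**Who is affected in the per-protocol set.** The subject must have a last Part A dose on or before about Day 89, take no later Part A dose, and still have an evaluable Week 16 mTLSS. Protocol 4.4 and 4.4.1 allow treatment to be interrupted without withdrawal, so an interruption still open at Week 16 fits this description.

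**Effect of the Week 16 on-site dose.** Suppose the Day 85 subject is dosed at the Week 16 visit. If that dose counts towards Part A, the SAP formula gives 86/113 = 76.1% and flags the subject. If it does not count, the formula gives 100%. SAP 11 does not say which applies.

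**Compliance table.** This table does not require Week 16 data. SAP 5.1 assumes 25–30% dropout. On about 105 subjects that is 0.25 × 105 = 26 to 0.30 × 105 = 32 after rounding. Any of them who dosed daily until leaving would be tabulated at 100%. How many would do so cannot be derived from the documents.

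**The case against.** The case for leaving the SAP as it stands has several good parts.

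- **The Week 16 requirement removes most early stoppers.** Subjects who discontinue are asked to attend an early-termination visit, and SAP 5.7 does not count that visit as Week 16. Those meeting the criteria in Protocol 4.4.2 are withdrawn. Those who start prohibited topical therapy for CHE in the first eight weeks are discontinued from study product and have their early-termination visit then (Protocol 6.4.3). This stands, and it is why the per-protocol gap is narrow.
- **On-site dosing exposes ordinary non-adherence.** A subject who stops at home after Day 60 but is dosed at the Week 12 visit has 61 doses over 85 days, or 71.8%, and is flagged. This also stands. The failure needs a gap with no later Part A dose.
- **Review is case by case.** SAP 7.2 calls these potential deviations, and the listings would show a long gap. This stands in part: a reviewer could catch the gap, but the computed percentage would not prompt it.
- **Protocol 7.1 concerns discontinuation and replacement, over the study treatment period.** It does not define the per-protocol set or limit itself to Part A. That is correct. A Part A scheduled-dose denominator combines Protocol 7.1 with SAP 7.2; neither states it alone.

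A reader might go further and infer that poor Part A compliers pass on the strength of a good Part B, or that active and placebo subjects are judged over different periods. For example, 78 of 112 Part A doses plus a perfect Part B gives (78 + 112)/224 = 84.8%. The documents do not support this inference. It requires pooling the two parts, whereas SAP 7.2 decides on Part A. There, 78/112 = 69.6% fails in every arm when the missed doses are scattered and dosing runs to the end of Part A. The introductory phrase in SAP 11 is ambiguous about period, but it is not a rule to pool.

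**Conclusion.** The concern holds in a limited form. The SAP 11 denominator differs from the one in Protocol 7.1, the difference is not declared in SAP 3.5, and the Part A rule in SAP 7.2 has no matching calculation. For a daily doser who stops, the formula returns 100% at any stop day.

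In the per-protocol set, the gap is confined to subjects whose dosing ends on or before about Day 89, does not resume within Part A, and who still have a Week 16 mTLSS. The number of such subjects cannot be estimated from the documents and is probably small. In the safety-population table the effect is wider, because early stoppers need no Week 16 data to be counted as compliant.

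The documents do not support a claim that early stoppers in general remain in the per-protocol set, or that the primary result is affected. The primary analysis uses the mITT population and the per-protocol analysis is supportive.

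These conclusions assume one scheduled dose per day, 112 Part A doses (110 to 114 with the visit window), and SAP 7.2 read as fixing Part A as the deciding period.

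**What to change.** In SAP 11, define Part A compliance as doses taken from Day 1 up to the Week 16 visit divided by doses scheduled in that period, identically for all arms. State that this figure drives the 80–120% rule in SAP 7.2 and hence the per-protocol set. Say whether the Week 16 on-site dose counts, and treat numerator and denominator alike. Keep the present ratio, relabelled as an on-treatment exposure description, and record the definition in SAP 3.5.

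The cost is one definition and one derived variable. Tablet counts at dispensing and return are already required (Protocol 6.2.1 and 6.3.2), and product is collected and dispensed at Week 16, so the records divide at that visit. The rule can be applied without treatment codes, as the blinded pre-lock review requires. The downside is that a few more subjects may leave the supportive per-protocol set.

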12 PHARMACOKINETIC ANALYSIS

Due to the sparse PK data collected from individual subjects, non-compartmental analysis will not be performed.

Descriptive statistics of the concentration data will be summarized based on nominal timepoints per dose level and will be presented in a table using the PK population. PK concentration data, including actual sampling time, will be provided in a listing. Concentration-time profiles (mean and individual) will be presented in figures.

PPD	STATISTICAL ANALYSIS PLAN, Version Final 1.0
Protocol Number: ASN002AD-202 V6.0	Sponsor: Asana BioSciences, LLC

For computation of mean plasma concentrations, data that are below the limit of quantification (BLQ) will be set to zero. However, BLQ data between two non-BLQ concentrations will be set to missing.

The analysis plan for population PK, PK/PD and population PK/PD analyses will be addressed elsewhere, and the results will be reported separately from the clinical study report.

PPD	STATISTICAL ANALYSIS PLAN, Version Final 1.0
Protocol Number: ASN002AD-202 V6.0	Sponsor: Asana BioSciences, LLC

13 EFFICACY ANALYSIS

13.1 Primary Efficacy Endpoint

The modified Total Lesion Symptom Score (mTLSS) will be assessed at the visits specified in Table 1. The mTLSS is an assessment of the severity of each of the following: erythema, scaling, lichenification/hyperkeratosis, vesicles, oedema, fissures and pruritus/pain. Each of these are rated using the 4-point severity scale described in [Table 2](#). Scores will be assigned for the most affected side (palmar or dorsal) of the most affected hand identified on Day 1. The same most affected side (palmar or dorsal) of the most affected hand will be followed throughout the study. These ratings are then added to create a total mTLSS calculated as the sum of assigned individual scores with a maximum value of 21 (most severe disease) and a minimum of 0 (no disease). The score will be set to missing in case of at least one missing value.

For exploratory purposes, a separate mTLSS will be evaluated for the feet for subjects for which the presence of foot eczema will be documented at the screening and Day 1 visits. Scores will be assigned for the most affected side (plantar or dorsal) of the most affected foot.

Additionally, the pruritus score portion of the mTLSS will also be analyzed for exploratory purposes.

PPD	STATISTICAL ANALYSIS PLAN, Version Final 1.0
Protocol Number: ASN002AD-202 V6.0	Sponsor: Asana BioSciences, LLC

Table 2. Modified Total Lesion Symptom Score

Parameter	Description of Severity ^a
Erythema	0 = Absent 1 = Faint erythema 2 = Prominent redness 3 = Deep intense red colour
Scaling	0 = Absent 1 = Slight flaking over limited areas, mostly fine scales 2 = Flaking over widespread area(s), coarser scales 3 = Desquamation covering over 30% of the hand, with coarse thick scales
Lichenification /hyperkeratosis	0 = Absent 1 = Mild thickening with exaggerated skin lines over limited areas 2 = Palpable thickening over widespread area(s) 3 = Prominent thickening over widespread area(s) with exaggeration of normal skin markings
Vesicles	0 = Absent 1 = Scattered vesicles affecting up to 10% of hand, without erosion 2 = Scattered or clustered vesicles affecting up to 30% of hand, without visible erosion or excoriation 3 = High density of vesicles extending over large area(s), or with erosion or excoriation
Oedema	0 = Absent 1 = Dermal swelling over less than 10% of hands 2 = Definite dermal swelling over more than 10% of hand 3 = Dermal swelling with skin induration over widespread area(s)
Fissures	0 = Absent 1 = Cracked skin affecting a small area of the hand 2 = Cracked skin affecting multiple areas of the hand and causing pain

PPD

STATISTICAL ANALYSIS PLAN, Version Final 1.0

Protocol Number: ASN002AD-202 V6.0

Sponsor: Asana BioSciences, LLC

	3 = One or more deep fissures and causing bleeding or severe pain
	0 = Absent
	1 = Occasional, slight discomfort a few times per day
Pruritus/pain	2 = Intermittent, causing discomfort frequently during the day
	3 = Persistent or interfering with sleep
^a 0 = absent; 1 = mild; 2 = moderate; 3 = severe.	

Descriptive statistics on hand mTLSS value will be presented by visit for each treatment group. Change from baseline and percentage change from baseline will be also summarized.

Primary Endpoint Analysis

Unblinded primary efficacy analyses will be performed after Week 16 is completed for all subjects. The CRO team and the sponsor will be unblinded after the database lock of Part A for the efficacy assessments, and a cleaning and monitoring of all safety data collected in Part A. The sites, investigators and subjects will remain blinded throughout the study. The primary efficacy analysis will be done using the mITT population and the PP population will be used as a supportive analysis.

A mixed effect model for repeated measures (MMRM) will be used to model the percent change from baseline in hand mTLSS. The model will include the stratification factor PGA score at baseline, if baseline PGA score is not highly correlates with baseline mTLSS score, treatment, visit and treatment-by-visit interaction as fixed effects and baseline hand mTLSS as a covariate. Primary comparison between Placebo and Treatment groups will be for Week 16 using contrasts. The unstructured (UN) variance-covariance matrix will initially be assumed. If the model does not converge using the UN covariance structure, the autoregressive (order 1) AR(1) structure will be used. If the AR(1) structure also does not converge, other covariance structures deemed appropriate to fit the data will be used. .

Distribution of residuals will be visually examined to determine whether substantial departures from normality and homogeneity of variance are apparent. If the data are inconsistent with the assumption of normality, either a normalizing transformation to the primary endpoint will be applied or a nonparametric analysis will be performed.

The same analysis will be performed on the per-protocol population.

Overall type 1 error control

PPD	STATISTICAL ANALYSIS PLAN, Version Final 1.0
Protocol Number: ASN002AD-202 V6.0	Sponsor: Asana BioSciences, LLC

For the primary endpoint of percent change-from-baseline in hand mTLSS at Week 16, a Hochberg step-up procedure adjustment will be done to test the two comparisons of interest (40mg vs. Placebo and 80mg vs. Placebo) as detailed in Section 6.5.

Sensitivity Analysis:

Additional sensitivity analyses will be performed for the primary endpoint - percent change from baseline in mTLSS using MMRM model described above and including all efficacy hand mTLSS data for these subjects (before and after the prohibited medication).

Subgroup Analysis:

Subgroup analysis by PGA strata will also be presented for the primary endpoint -percent change from baseline in mTLSS. MMRM model will be used with treatment, visit and treatment-by-visit interaction as fixed effects, and baseline hand mTLSS as a covariate and primary comparison will be performed at Week 16.

